4.5.3. Per Protocol (PP)

The per protocol population will comprise subjects who have received Day -7 of cemiplimab, the injection of Ad-RTS-hIL-12 with at least one post IL-12 dose of veledimex, at least one post IL-12 dose of cemiplimab (e.g., Day 15), and who have not had a major protocol deviation for which the key efficacy endpoints could be regarded as confounded or uninterpretable. Subjects who have had minor protocol deviation(s) that are thought not to impact efficacy will be included in this analysis population. Estimates of the overall OS hazard rate, the OS at prespecified timepoints, PFS and the ORR will be based on the PP population.

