4.5.4. Evaluable Safety Population (ESP)

The ESP is a subset of the FAS. Regardless of major protocol deviations, these subjects have received at least one of the following:

- Day -7 of cemiplimab,
- the injection of Ad-RTS-hIL-12 with at least one post IL-12 dose of veledimex,
- and at least one post IL-12 dose of cemiplimab (e.g., Day 15).

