4.7.1. Overview of Statistical Summaries by Defined Populations

Subject populations will be evaluated and used for presentation and analysis of the following:

- The FAS will be used for summaries of subject disposition, baseline characteristics and for safety. In addition, the FAS will be used in secondary analyses of OS, ORR, and PFS.
- The PP population is to be used for the primary analysis of OS, ORR, PFS and OS.
- When applicable the ESP will be used for analysis of dose limiting toxicities.
- [REDACTED]

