Table 14.3.1.13	Treatment-Related Treatment Emergent Adverse Events by Preferred Term in Decreasing Frequency	Full Analysis Population	AEPT			AE	ADAE	AEPT tables are done
Table 14.3.4.1	Listing of Abnormal Laboratory Values		Sig_lab		LAB_NORMLAB/ LBCHEM1/ LBCOAG1/ LBHEMA1/ LBTHYR/LBURIN1 /LBURIN2	LB	ADLB	
Table 14.3.4.2	Listing of Clinically Significant Laboratory Values		Sig_lab			LB	ADLB	
Table 14.3.5.1	Ad-RTS-hIL-12 Injections	Full Analysis Population	Exp1			EX/EC	ADEX	
Table 14.3.5.2	Veledimex Exposure	Full Analysis Population	Exp2			EX/EC	ADEX	
Table 14.3.5.3	Cemiplumab Exposure	Full Analysis Population	Exp3			EX/EC	ADEX	
Table 14.3.6.1	Summary of Serum Chemistry Results	Full Analysis Population	Lab			LB	ADLB	
Table 14.3.6.2	Clinical Significance of Serum Chemistry Results	Full Analysis Population	Lab2			LB	ADLB	
Table 14.3.6.3	Summary of Hematology Results	Full Analysis Population	Lab			LB	ADLB	
Table 14.3.6.4	Clinical Significance of Hematology Results	Full Analysis Population	Lab2			LB	ADLB	
Table 14.3.6.5	Summary of Coagulation Results	Full Analysis Population	Lab			LB	ADLB	
Table 14.3.6.6	Clinical Significance of Coagulation Results	Full Analysis Population	Lab2			LB	ADLB	
Table 14.3.6.7	Summary of Urinalysis Results	Full Analysis Population	Lab			LB	ADLB	
Table 14.3.6.8	Clinical Significance of Urinalysis Results	Full Analysis Population	Lab2			LB	ADLB	
Table 14.3.7	Summary of KPS	Full Analysis Population	KPS			QS	ADQS	
Table 14.3.8	Summary of Vital Signs	Full Analysis Population	Vitals					
Table 14.3.9	Summary of Weight	Full Analysis Population	Weight					
Table 14.3.10	Targeted Neurological Exam	Full Analysis Population	Neuro					
Table 14.3.11	ECG Findings	Full Analysis Population	ECG1			EG	ADEG	
Table 14.3.12	Summary of ECG Results	Full Analysis Population	ECG2			EG	ADEG	
Table 14.3.13	Dose Limiting Toxicities	Per Protocol Population	DLT					
Figure 14.2.3	Kaplan Meier plot of Progression Free Survival by Veledimex Dose							
Figure 14.2.4	Kaplan Meier plot of Overall Survival by Veledimex Dose							
Figure 14.2.5	Kaplan Meier plot of Progression Free Survival by Group							

Figure 14.2.6	Kaplan Meier plot of Overall Survival by Group						
Figure 14.2.7	Forest Plot	Per Protocol Population	FPLT				
Listing 16.2.1	Subject Disposition	Full Analysis Population	L_Disp				

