Listing 16.2.3.1	Eligibility	Full Analysis Population	L_Elig				
Listing 16.2.3.2	Subject Population	Full Analysis Population	L_Pop				
Listing 16.2.2	Protocol Deviations	Full Analysis Population	L_Dev				
Listing 16.2.4.1	Demography and Baseline Characteristics	Full Analysis Population	L_Demo				
Listing 16.2.4.2	Medical and Surgical History	Full Analysis Population	L_Mhx				
Listing 16.2.4.3	High Grade Glioma Diagnosis	Full Analysis Population	L_Hgg				
Listing 16.2.4.4	Prior Cancer Treatment	Full Analysis Population	L_PriCnt				
Listing 16.2.4.5	Previous Medications	Full Analysis Population	L_Conm				
Listing 16.2.4.6	Concomitant Medications	Full Analysis Population	L_Conm				
Listing 16.2.4.7	Corticosteroid Dosage	Full Analysis Population	L_CDD				
Listing 16.2.4.8	Post Treatment Anti-Cancer Therapy	Full Analysis Population	L_PostCnt				
Listing 16.2.4.9	Concurrent Medical Procedures	Full Analysis Population	L_Npmcd				
Listing 16.2.5.1	Ad-RTS-hIL-12 Injection	Full Analysis Population	L_DS1				
Listing 16.2.5.2	Veledimex Capsule Diary	Full Analysis Population	L_DS2				
Listing 16.2.5.3	Veledimex Dose Modification	Full Analysis Population	L_DS3				
Listing 16.2.6.1	Pre-Baseline Lesion Assessment	Full Analysis Population	L_Pbla				
Listing 16.2.6.2	Assessment of Target Lesions	Full Analysis Population	L_Tar				
Listing 16.2.6.3	Assessment of Non-Target Lesions	Full Analysis Population	L_NTar				
Listing 16.2.6.4	Non-Enhancing Lesions	Full Analysis Population	L_Nenh				
Listing 16.2.6.5	Evaluation of Overall Response	Full Analysis Population	L_Tovr				
Listing 16.2.7.7	Dose Limiting Toxicities	Full Analysis Population	L_Dlt				
Listing 16.2.7.1	Adverse Events	Full Analysis Population	L_Ae				
Listing 16.2.7.2	Treatment Emergent Adverse Events	Full Analysis Population	L_Ae				
Listing 16.2.7.3	Serious Adverse Events	Full Analysis Population	L_Ae				
Listing 16.2.7.4	TEAEs leading to Study Drug Dose Modification	Full Analysis Population					
Listing 16.2.7.5	TEAEs leading to Study Discontinuation	Full Analysis Population	L_Ae				
Listing 16.2.7.6	TEAEs with CTCAE Toxicity Grade ≥ 3	Full Analysis Population					
Listing 16.2.7.8	Deaths	Overall Safety Population	L_Deat				
Listing 16.2.6.6	Survival	Full Analysis Population	L_Surv				
Listing 16.2.6.7	Progression Free Survival Data	Full Analysis Population	L_Pfs				
Listing 16.2.6.8	Kaplan Meier Survival and Censoring Times	Full Analysis Population	L_Surv2				

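### SAP Table 14.3.13 puts dose-limiting toxicities on the Per Protocol population, against the ESP in Section 4.7.1 and the FAS in its own listing and in Section 9

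*SAP*

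**What the plan says.** The population for dose-limiting toxicities (DLTs) is stated in three different ways.

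- **Table 14.3.13**, titled "Dose Limiting Toxicities", in both lists of tables, listings and figures in the SAP appendices: "Dose Limiting Toxicities Per Protocol Population". It is the only table in the 14.3 safety series labelled PP. The others that name a population are on the FAS.
- **SAP 4.7.1**: "When applicable the ESP will be used for analysis of dose limiting toxicities".
- **Listing 16.2.7.7**, in both lists: "Dose Limiting Toxicities Full Analysis Population".

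Two general rules also apply. SAP Section 9 places every safety analysis on the FAS, adding the ESP where applicable. Protocol 16.6.2 uses the safety population (any dose of any agent) for every safety variable.

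Membership is defined in SAP 4.5. Besides the Day -7 cemiplimab dose, the injection and one later veledimex dose, PP requires "at least one post IL-12 dose of cemiplimab (e.g., Day 15), and who have not had a major protocol deviation". The ESP opens with "Regardless of major protocol deviations, these subjects have received at least one of the following", then lists three exposures, the last of which is joined by the word 'and'. The FAS takes anyone who received a dose of any study drug; SAP 4.4 gives its size as 40.

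**The concern.** Whether a subject gets cemiplimab after the injection depends partly on how treatment was tolerated. Protocol Table 3 provides for permanent discontinuation of cemiplimab after listed severe reactions, and the Protocol 10.9 toxicity window opens at Day -7, before that dose is due. Restricting a toxicity table to subjects who got the dose therefore conditions the toxicity rate on something toxicity can prevent. A subject who dies, or stops for good, before any post-injection cemiplimab is missing from both the count and the base.

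Safety is half of the primary objective, and the trial is single-arm and open-label. With three populations named, the choice of denominator could also be made after the data are known.

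**Working it through.** **1. Is there a stated figure to reproduce?** There is none for DLTs: the documents give no DLT count, DLT rate or PP size. The nearest stated toxicity figures are the operating characteristics in SAP 4.1. An exact binomial recursion over looks at 5, 10, 15, 20 and 25 subjects, with crossing taken as a count above the listed value, reproduces them. For the lower boundary, the crossing probability is 0.101 at a 30% toxicity rate and 0.943 at 60%, with expected sample sizes 23.8 and 11.9. For the upper boundary it is 0.074 and 0.932. That boundary counts subjects who meet the Protocol 10.9 stopping criteria. It does not draw on Table 14.3.13, so the population conflict leaves it unchanged.

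**2. Who is in which population?** Take subjects who received Day -7 cemiplimab and the injection.

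| Subject | FAS | PP | ESP, any one exposure | ESP, all exposures |
|---|---|---|---|---|
| Dies or stops for good before any post-injection cemiplimab | in | out | in | out |
| Stops veledimex early after at least one post-injection dose, later gets cemiplimab, no major deviation | in | in | in | in |
| Post-injection veledimex taken, next cemiplimab delayed but given, no major deviation | in | in | in | in |
| All required doses, with a major deviation | in | out | in | in |

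The first row is the problem. It also shows why the ESP does not resolve it. The opening words "these subjects have received at least one of the following" make the ESP practically the FAS, because treatment starts with Day -7 cemiplimab. The closing 'and' makes it PP without the deviation criterion, which removes the same early-stopping subjects.

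**3. Direction of the effect.** Let N be the FAS size, d the subjects with a DLT, m the subjects excluded from PP, and e those of the m who had a DLT.

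- FAS rate = d/N
- PP rate = (d − e)/(N − m)
- PP rate < FAS rate when N(d − e) < d(N − m), that is, when e/m > d/N.

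So PP understates the rate exactly when DLTs are more common among the excluded than overall. That is the expected direction if toxicity is why the dose was not given. If subjects are excluded for other reasons, the PP rate can be the higher one.

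**4. Size, on assumed inputs.** N = 40 is from SAP 4.4; d, m and e are assumptions. With d = 6, the FAS rate is 6/40 = 15.0%.

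With m = 4 (PP base 36):

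- e = 0: 6/36 = 16.7%
- e = 1: 5/36 = 13.9%
- e = 2: 4/36 = 11.1%
- e = 3: 3/36 = 8.3%
- e = 4: 2/36 = 5.6%

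With m = 11, the planned gap between accrual and evaluable subjects (36 − 25, Protocol 16.2), the PP base is 29:

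- e = 0: 6/29 = 20.7%
- e = 2: 4/29 = 13.8%
- e = 4: 2/29 = 6.9%
- e = 6: 0/29 = 0%

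**The case against.** **The row may be an uncleaned shell.** The same lists contain items that do not fit this single-dose trial, such as survival for a 20 mg main study with an expansion group, and Kaplan-Meier plots by veledimex dose. They also keep vital-sign, neurological and ECG tables that SAP 10.6 says will not be produced. The row for Table 14.3.13 has no dataset or completion entry, while the adverse-event tables are marked done. The lists come from a spreadsheet, so strike-through or other marking may have been lost. Section 4.7.1 itself says only 'when applicable'. All of this stands, and it lowers the severity. It does not reconcile the three labels.

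**Safety is otherwise reported on all treated subjects.** This also stands. FAS tables cover all treatment-emergent events, related events, grade 3 or higher, serious events, discontinuations and deaths, and the DLT listing is on the FAS. No event is hidden, and no decision rule uses this table. A reader might infer that the trial's toxicity as a whole is understated; the documents do not support that.

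**PP does not require completing the early treatment window.** A reader might infer that missing the Day 15 visit, or stopping veledimex early, removes a subject. It does not. One post-injection veledimex dose is enough, Day 15 is only an example, and Protocol 8.1 allows delays of up to 14 days for toxicity. Only subjects who never receive a later cemiplimab dose leave on this criterion.

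**The deviation criterion is less firm.** SAP 4.7.2 says that, in general, no subject was to be removed from a population for a deviation, which sits badly with the PP definition. The argument here rests on the dosing criterion and does not need the other.

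**Conclusion.** The PP label on Table 14.3.13 is wrong as written. It contradicts SAP 4.7.1, its own listing, SAP Section 9 and Protocol 16.6.2, and it excludes by definition subjects whose toxicity prevented any post-injection cemiplimab. The severity is minor, because one summary table is affected and the same events appear elsewhere on the FAS.

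The size cannot be known from the documents. On the assumption of 6 DLTs in 40 and 4 exclusions, the PP rate runs from 16.7% to 5.6% against 15.0%. It would be tempting to quote 15.0% against 5.6% as the bias, but that is the extreme case in which all 4 excluded subjects had a DLT; with none, PP is the higher figure.

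Two further readings go beyond the text. The ESP is not plainly the FAS: its wording is ambiguous. Nor can DLTs be taken to be the Protocol 10.9 events. The readable text of neither document defines a DLT or a DLT window for this trial, so equating the two would supply a rule the documents do not contain.

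**What to change.** - If Table 14.3.13 is produced, label and run it on the FAS, in line with Listing 16.2.7.7, SAP Section 9 and Protocol 16.6.2.
- Change SAP 4.7.1 to name the same population.
- Delete the ESP, or restate it so that it is clear whether one exposure or all three are required. If it is deleted, remove the reference to it in Section 9.
- Ask the sponsor to state the DLT definition and window used for this table, or to drop the table and its listing.

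The first three changes are one table label, one sentence and one definition (with its cross-reference), and need no new data. The DLT definition is a separate request. If none was in use during the trial, dropping the output is the cheaper course, and the FAS adverse-event tables already cover the events.
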